### **8.3.4.2 Analysis of Immune Endpoints**

#### Immune Cell Activation

For each arm individually, flow cytometry of circulating immune cell subsets will also be performed on pre-treatment blood and again after 9 weeks on vorinostat (post epigenetic priming). Established flow cytometry panels will examine T cell activation. Immune cell quantification will be summarized by changes from baseline to after treatment using descriptive statistics. Furthermore, paired Wilcoxon signed-rank test will be applied to test the pre-post treatment changes. When available, immune cells digested from resected tumor tissues will also be assessed by flow cytometry.

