### 1.5 Correlative Studies

Immune checkpoint inhibitors have revolutionized cancer therapy, yet have limited efficacy in estrogen receptor (ER+) breast cancer. Implicated factors include scarcity of tumor-infiltrating lymphocytes (TILs), low PD-L1 expression, female gender, and liver involvement. In vitro and in vivo studies suggest that epigenetic modulation with HDAC inhibitors modulate regulatory T cells (Treg) and change TIL composition, which is further associated with the presence of a specific immune signature.

Patients with ER+ metastatic breast cancer, who progressed on multiple prior therapies, were treated with tamoxifen in combination with vorinostat and pembrolizumab either immediately or after 3 weeks of epigenetic priming in a phase II trial. Comprehensive flow-cytometric immunophenotyping, PD-L1 staining, and histone acetylation were evaluated on tumor and blood cells.

34 patients (median age 56 years (32-81), heavily pretreated with a median of 5 (2-13) prior regimens received at least one dose of vorinostat and evaluable for response. Grade  $\frac{3}{4}$  toxicities in 2 pts each (6%) included immune hepatitis, fatigue, and thrombocytopenia. Grade 2 toxicities were pneumonitis and colitis in 3%, fatigue in 27% and thrombocytopenia in 12% pts. Six patients did not receive pembrolizumab due to rapid progression or toxicity. Clinical benefits rate defined as CR, PR, and stable disease  $> 6$ m was seen in 5/28 (18%) of patients. Tumor lymphocyte infiltration and PD-L1 expression were low. High expression of PD-1/CTLA-4 dual staining in CD8 cells of  $>20\%$  in tumor or blood was seen in 5 patients overall, 4/5 (80%) patients with benefit and in one other patient, who was withdrawn due to immune hepatitis in week 3. Both tumor and peripheral blood CD8 PD-1/CTLA-4 dual expression strongly correlated with time to progression and reduction in Foxp3+/CTLA-4high Treg population in tumors by vorinostat.

Our data highlight the potential for patient selection based on exhausted CD8+ cells in blood or tumor to predict response to immune checkpoint inhibitors in a small subset of ER+ breast cancer patients (NCT02395627).

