## 2.4 Exploratory (Correlative) Objectives

Exploratory Objective	Endpoint(s)
1. Evaluation of biomarker target threshold on response rate (retrospective cut off of 20% vs 10%)	Biomarker target threshold on response rate
2. To assess the ratio of effector T cells: regulatory T cells in blood and tumor biopsies pre- and post-therapy.	Ratio of effector T cells: regulatory T cells in blood and tumor biopsies pre- and post-therapy
3. To evaluate inflammatory T cell signature changes in blood and tumor biopsies pre- and post-therapy.	inflammatory T cell signature changes in blood and tumor biopsies pre- and post-therapy
4. To evaluate changes in number of myeloid-derived suppressor cells (MDSCs) in peripheral blood and tumor biopsies pre- and post-therapy.	changes in number of myeloid-derived suppressor cells (MDSCs) in peripheral blood and tumor biopsies pre- and post-therapy
5. To evaluate changes in histone acetylation in peripheral blood cells and tumor biopsies pre- and post-therapy	changes in histone acetylation in peripheral blood cells and tumor biopsies pre- and post-therapy
6. Initial comparison to vorinostat-induced PD-1 in lymphocytes, PD-L1 modulation	Comparison to vorinostat-induced PD-1 in lymphocytes, PD-L1 modulation
7. Nanostring and 10x sequencing and single cell immune phenotyping (on stored tissue for successful arms only)	Completion of Nanostring and 10x sequencing and single cell immune phenotyping (on stored tissue for successful arms only)
8. Impact of HDAC inhibition of response to pembrolizumab vs. pembrolizumab in biomarker enriched population	Impact of HDAC inhibition

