**Table 5.2 Arm A Regimen Description**

Investigational Product	Premedication; precautions	Dose	Route	Schedule	Cycle Length
Pembrolizumab	No premedications No precautions	200 mg	Intravenous	Day 1, Week 1 Cycles 1+	3 weeks (21 days)
Vorinostat	Administer whole with food, if possible	400 mg	Oral	Days 4 of 7 days All cycles	
Tamoxifen	No premedications No precautions	20 mg (tablets)	Oral	Daily continuous All cycles	

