## 6.1 Study Calendar

Period/ Procedure	Pre- Screening	Screening 	Cycle 1			Cycle 2	Future Cycles 	Restaging or Off-Study Visit Survival Follow-up
Study Day/Visit Day*	-365 to -28	-28 (±3)	1 (±3)	10-12 (±3)	15 (±3)	1 (±3)	1 (±3)	9 weeks Post Start of Tx (±7)
Study Treatment/Drug Administration								
Pembrolizumab			200 mg q every 3 weeks; start on C1D1					
Vorinostat			400 mg once a day, 4 days on, 3 days off, weekly every cycle					
Tamoxifen			20 mg once a day continuously					
Administrative Procedures								
Prescreening ICF	X							
Informed consent		X						
Clinical Assessments								
Physical exam		X	X		X	X	X	
Vital signs		X	X		X	X	X	
Performance status		X	X		X	X	X	
Medical history		X						
Concomitant medications		X	X		X	X	X	
Toxicity Assessment 		X	X		X	X	X	X 
Drug Diaries 			X			X	X	
Documentation of Response		X					X	

 All screening procedures must be performed within 28 days unless otherwise indicated. Pre-study tests, History and Physical may be used for Day 1 tests if within 2 weeks

 Cycle delays up to 14 days for non-medical reason (e.g. holidays) are acceptable without notification of regulatory agencies

 Therapy delay for palliative radiation should be based on discussion with the study sponsor and the treating physician, every effort should be made not to hold therapy, patients, where vorinostat is being held for more than 4 weeks, may stay on study if there is felt to be a benefit

 Toxicity assessment must be performed until all treatment-related toxicities have been resolved or decreased to grade 1. Adverse events must be recorded up to 30 days after termination on study

 Drug diaries will be administered for vorinostat and tamoxifen (oral drugs) only on the first day of every cycle

Period/ Procedure	Pre- Screening	Screening 	Cycle 1			Cycle 2	Future Cycles 	Restaging or Off-Study Visit Survival Follow-up
Study Day/Visit Day*	-365 to -28	-28 (±3)	1 (±3)	10-12 (±3)	15 (±3)	1 (±3)	1 (±3)	9 weeks Post Start of Tx (±7)
Laboratory Assessments								
Hematology 		X	X		X	X	X	
Comprehensive Metabolic Panel 		X	X		X	X	X	
Thyroid Function 		X				X	X (odd cycles)	
Tumor Markers 		X	X			X	X	
Pregnancy test 		X					X	

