## 6.4 Correlative Studies

### 6.4.1 Histone Acetylation in peripheral blood mononuclear cells

Exposure to HDAC inhibitors results in inhibition of histone deacetylation. Histone acetylation (mainly histone H3) has been used as a biological marker of HDAC inhibitor activity. H3 acetylation has been measured successfully in PBMCs in clinical trials using vorinostat and other HDAC inhibitors. We will, therefore, measure H3 and H4 acetylation in peripheral blood mononuclear cells and tumor samples of patients before and after treatment with vorinostat.

Mononuclear cells will be obtained prior to treatment initiation and repeated on day 10 (+2) and at the end of cycle 3 (day 17-19). Cells will be isolated from patient blood by centrifugation at 400 x g (Sorvall, HS4 rotor) for 30 min using a Ficoll-Paque gradient (Sigma, St. Louis, MO) as described by Sandor et al. Histone acetylation will be quantified by WB analysis of PBMCs using an acid extraction method to collect nuclear histone proteins.

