### 6.4.3 Logistics on Immune modulation

For immune assays we will collect 60cc of blood in green top tubes at baseline and day 10-12 in cycle 1 and on day 17-18 in cycle 3, at the time points specified above for tumor biopsies, FFPE for immune cell infiltrate and a frozen section will be obtained for TCR sequencing.

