#### T cell Receptor (TCR) Deep Sequencing

The change in tumor-infiltrating TCR between pre-treatment and post-epigenetic priming will be assessed by calculating the number of unique clonotypes comprising the top 25th percentile of cumulative reads after sorting by clone abundance. Repertoire change between sequencing experiments will be measured using Morisita's distance. This analysis will also be performed in subjects receiving adjuvant chemotherapy using the same statistical techniques to evaluate the impact of adjuvant MPDL3280A on circulating T cell repertoire remodeling.

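### Every on-treatment sample follows pembrolizumab, yet 8.3.4 labels marker changes as priming and tests them only within arms, so vorinostat's added effect is never estimated

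*Combined protocol and SAP*

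**What the plan says.** **Schedule.** The Study Calendar (6.1) gives pembrolizumab as "200 mg q every 3 weeks; start on C1D1". Table 5.2 lists it in Arm A as "Day 1, Week 1 Cycles 1" and onward, and Table 5.3 does the same for Arm B. Vorinostat is given in Arm A only, 4 days of every 7 in all cycles, with no run-in. The pilot differed: its patients received pembrolizumab "either immediately or after 3 weeks of epigenetic priming in a phase II trial" (1.5).

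**Samples.** Section 3.1 calls for follow-up biopsy and blood from all patients at 8 to 10 weeks. Section 6.4.1 takes mononuclear cells before treatment, "repeated on day 10 (+2) and at the end of cycle 3 (day 17-19"). Section 6.4.3 puts the late blood draw "on day 17-18 in cycle 3".

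**Analysis.**
- Section 8.3.4.2 (Immune Cell Activation) takes each arm by itself, repeats flow cytometry "again after 9 weeks on vorinostat (post epigenetic priming"), and applies a paired signed-rank test. The antibody analysis uses the same nine-week vorinostat label.
- Section 8.3.4.1 uses the priming label too. The change in T-cell receptors "between pre-treatment and post-epigenetic priming will be assessed", and the tumor DNA analysis is labelled in the same way.
- The Tumor PD-L1 Assessment text in 8.3.4.1 describes Arm A as the arm in which pembrolizumab is delayed.

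**Assay restriction.** Objective 7 in 2.4 plans Nanostring, 10x sequencing and "single cell immune phenotyping (on stored tissue for successful arms only"). *Successful* is not defined.

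**The concern.** A sample can be called post-priming only if priming came first. Here vorinostat and pembrolizumab begin together, so the label describes a design this trial does not have. For Arm B it describes a drug the patients never receive.

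Section 1.3.1.2 says the pilot could not tell whether benefit came from the biomarker alone or from the biomarker together with HDAC-inhibitor effects on regulatory T cells. The randomized Arm B is what allows this trial to do better. If marker change is analyzed only within arms, that advantage goes unused for the correlates, and a change driven by pembrolizumab could be written up as epigenetic priming. The restriction in objective 7 adds to this, because the protocol (2.1) expects Arm B to stop at 11 patients.

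**Working it through.** **1. Which drugs precede each sample.** With 21-day cycles, pembrolizumab falls on days 1, 22 and 43. The cycle 1 day 10-12 sample follows one infusion. Cycle 3 day 17-19 is study day 42 + 17 to 42 + 19 = 59 to 61, after three infusions. No post-baseline sample precedes pembrolizumab in either arm.

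**2. Is any between-arm test of marker change planned?** Going through 8.3.4:
- PD-L1: a logistic model that includes arm, but its outcome is tumor response.
- Tissue immune subsets: descriptive.
- mRNA and copy number: paired pre/post tests, and responders against non-responders.
- Flow cytometry: paired test within arm.
- Antibodies: responders against non-responders.

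None compares change between arms. The PD-L1 text also predicts that expression will not be associated with treatment because vorinostat stimulates it. That reasoning fits a trial in which both arms receive vorinostat; here only Arm A does.

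**3. What a significant Arm A change would mean (illustration).** Assume no vorinostat effect and a shift of *d* SDs of the paired change from the other drugs and time. The documents give no such figure, so a range is shown. A paired *t* test at two-sided 0.05 stands in for the signed-rank test, with noncentrality d√n.
- n = 35, d = 0.5: 0.5 × √35 = 2.96, 34 df, P(significant) = 0.82.
- n = 35, d = 0.3: 0.3 × √35 = 1.77, P = 0.41.
- With 28 pairs (80% of 35, also an assumption): 0.72 and 0.33.

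**4. Objective 7: how often control data would exist.** Inputs from 8.1.1: Arm A stops with 2 or fewer responses in 13; Arm B stops with 1 or fewer in 11 and rejects its null with 7 or more in 30; expected rates are 0.40 and 0.10.
- Check against the plan: P(46 enrolled) = P(A continues) × P(B stops) = 0.942 × 0.697 = 0.657, against the stated figure of about 65%. It reproduces. Arm B type I error is 0.022 and power 0.900, consistent with the stated 0.025 and 0.9.
- P(B passes stage 1 at 0.10) = 1 − 0.9¹¹ − 11 × 0.1 × 0.9¹⁰ = 1 − 0.314 − 0.384 = 0.303.
- P(B rejects) = Σ P(X₁ = x) P(X₂ ≥ 7 − x) over x = 2 to 11, with X₁ ~ Bin(11, p) and X₂ ~ Bin(19, p).

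| Arm B true rate | Passes stage 1 | Rejects its null |
|---|---|---|
| 0.10 | 0.30 | 0.02 |
| 0.35 | 0.94 | 0.90 |

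**5. What the between-arm contrast can detect.** Differences are in SDs of change, two-sided 0.05.
- 35 vs 11 (the expected path): √(1/35 + 1/11) = 0.346. For 0.5 SD the noncentrality is 0.5/0.346 = 1.45 on 44 df, so power is 0.29. Detectable at 80% power (normal approximation): 2.80 × 0.346 = 0.97 SD.
- 35 vs 30: √(1/35 + 1/30) = 0.249. Detectable: 2.80 × 0.249 = 0.70 SD.

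**The case against.** **The objectives mostly ask for pre/post change.** This stands. Objectives 2 to 5 are worded as change before and after therapy, without attribution to vorinostat, and a within-arm paired test answers them. The gap concerns objective 6, which names a vorinostat-induced effect, and the marker side of objective 8. Response itself is compared between arms in 8.3.2.

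**The paired test is not wrong.** This also stands. If treatment moves a marker, a significant result is correct; the fault lies in the label. A reader might take 82% as a false-positive rate of the planned test. It is not one: it shows how little a significant Arm A change says about vorinostat. Parallel Arm B results would give a careful reader a warning, but two separate within-arm tests do not estimate a difference.

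**Control tissue is sequenced anyway.** A reader might infer from objective 7 that Arm B tissue would almost never be sequenced. The documents do not support that. The restriction covers Nanostring, 10x and single-cell phenotyping. T-cell receptor sequencing (6.4.3, 8.3.4.1) carries no such condition, DNA copy number and sequencing cover each cohort, and flow cytometry is planned for each arm. The 2% holds for only one meaning of *successful*.

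**Sampling days.** A reader might infer that days 12 and 19 are off-drug. Counting 4 on and 3 off from day 1 gives on-days 8-11 and 15-18, which exclude both. Counting from day 2 gives 9-12 and 16-19, which include both. No section fixes which 4 of 7 days are dosed, and 6.4.2 already ties the cycle 3 samples to the vorinostat morning dose. What remains is a mismatch between day 17-19 (6.1, 6.4.1, 6.4.2) and day 17-18 (6.4.3).

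**The contrast does not isolate priming.** Correct. With a concurrent start, the difference between arms estimates what vorinostat adds. It cannot separate priming from vorinostat's other effects.

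**Conclusion.** The point holds for labelling and for the missing comparison. The schedule provides no sample on vorinostat without pembrolizumab, the priming label does not fit the samples and cannot apply to Arm B, and 8.3.4 contains no between-arm test of marker change. An Arm A pre/post change therefore cannot be attributed to vorinostat. The 82% and 41% rest on assumed shifts, complete pairs in 35 patients and a *t* approximation.

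For Nanostring, 10x and single-cell assays, control data would exist in 2% to 30% of trials at the Arm B rate the protocol expects, and in 90% to 94% at its design alternative, depending on what *successful* means.

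The effect is confined to exploratory work. The primary analysis, the stopping rules and the secondary endpoints are unaffected. It is worth correcting because the samples are already planned in both arms.

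**What to change.** 1. In 8.3.4, rename the post-baseline time points *on treatment* and remove the vorinostat and priming labels, in particular where they cover Arm B.
2. Add the between-arm difference in change from baseline for the markers under objectives 6 and 8: ANCOVA of the follow-up value on baseline and arm, or a rank-sum test on changes. Describe it as vorinostat's added effect, not as a test of priming. Keep the within-arm paired tests as descriptive.
3. In objective 7, drop the restriction to successful arms and run any Nanostring, 10x or single-cell assay on stored pairs from both arms.
4. Reconcile the PD-L1 text in 8.3.4.1 with the start day in 6.1, and its prediction about treatment with the fact that only Arm A receives vorinostat. Reconcile the cycle 3 sampling days in 6.1, 6.4.1 and 6.4.2 with those in 6.4.3 and with the vorinostat dosing days. No view is taken here on which schedule is right.

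**Cost.** Items 1, 2 and 4 are changes of wording. Item 3 adds assays on Arm B pairs, at most 11 on the expected path. The main drawback is precision: about 29% power for a 0.5 SD difference at 35 vs 11, so the contrast should be reported as an estimate with its confidence interval, and a null result should not be read as no effect.

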#### Circulating Antibody Detection and Characterization

Spotted antigen arrays will be used to detect circulating antibodies will be performed on sera derived from the pretreatment and after 9 weeks on vorinostat. After standard preprocessing of the protein array data, Cluster and Treeview software will be used for unsupervised clustering of the data with Pearson correlation and complete linkage. For each array, an antigen is identified

as being detected if its value is above the median. To determine the number of up- and down-modulated antibodies, the difference in log2 intensity values of pretreatment and post-treatment samples will be taken for each patient to identify antigens that are detected differentially due to treatment. Number of antibodies with at least 2- or 4-fold difference between pretreatment and post-treatment samples will be compared between clinical responders and nonresponders by performing two-sided Wilcoxon rank sum test.

All correlative studies and assays will be performed in the [name] lab, in conjunction with Merck, with the help of [name] and other experts in the field.

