## 3 Study Design

### 3.1 Characteristics

We propose a single site Phase II, two-arm, open-label unblinded, 65-patient trial in patients with hormone therapy-resistant breast cancer (HTR) to test the role of epigenetic priming in a biomarker enriched patient population in HTR breast cancer. The two arms include Arm A: pembrolizumab, vorinostat, and tamoxifen and Arm B pembrolizumab and tamoxifen.

Patients will be evaluated for response at 9 weeks ( $\pm 1$  week) by RECIST1.1 (using IR-RECIST) and will continue on therapy if they have stable disease or response at the time of disease evaluations. Patients with progression on imaging but are clinically stable, may stay on study but will require follow-up staging after 4-6 weeks. Patients will be assessed continually for safety and tolerability as well as for any adverse events. If progression on therapy with pembrolizumab, patient may continue if clinically indicated and be re-evaluated after 4-8 weeks.

We will follow AEs of clinical interest as defined by Merck and will dose modify pembrolizumab as per Merck guidelines. We have significant prior experience with vorinostat, tamoxifen, and pembrolizumab combination and are facile with managing drug toxicities.

Tissue biopsies of all patients will be collected prior to enrollment to assess for pre-treatment of our immune signature and PD-L-1 expression. Follow up biopsies and peripheral blood collection will be taken from all patients post-treatment at 8-10 weeks to characterize changes in local tissue effects and antigen-specific cellular and humoral immune responses in peripheral blood.

Patients will be stratified by prior number of hormonal and chemotherapies.

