### 8.1 Sample Size Considerations

#### 8.1.1 Sample Size and Power Estimate

For Arm A (pembro + vorinostat + TAM): The null hypothesis that the true response rate for pembrolizumab and vorinostat in ER+ pretreated patients alone without biomarker enrichment is 0.15 which will be tested against the alternative that response rate of pembrolizumab in a biomarker select population is 0.40. In the first stage, 13 patients will be accrued. If there are 2 or fewer responses in these 13 patients, the study will be stopped. Otherwise, 22 additional patients will be accrued for a total of 35. The null hypothesis will be rejected if 10 or more responses are observed in 35 patients. This design yields a type I error rate of 0.025 and power of 0.9 in this treatment arm when the true response rate is 0.4 in this patient subpopulation.

For Arm B (pembro + TAM): The null hypothesis that the true response rate for pembrolizumab in ER+ pretreated patients alone is 0.10 which will be tested against the alternative that response rate of pembrolizumab in a biomarker select population is 0.35. In the first stage, 11 patients will be accrued. If there are 1 or fewer responses in these 11 patients, the study will be stopped. Otherwise, 19 additional patients will be accrued for a total of 30. The null hypothesis will be rejected if 7 or more responses are observed in 30 patients. This design yields a type I error rate of 0.025 and power of 0.9 in this treatment arm when the true response rate of pembro and TAM treatment is 0.35 in this patient subpopulation.

Based on earlier results in Section 1.3 and hypothesized treatment effects, we will most likely to enroll 46 evaluable patients (~65% chance), whereas the possible enrollment ranges from 24 to 65. For the comparison of the treatment arms, the proposed design will have 72.53% power for the Fisher's exact test at 0.1 significance level when the true response rates are 0.4 and 0.1 for the immune priming and the no immune priming treatment arm.

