##### Immune Cell mRNA Signatures of Response

To identify individual genes whose expression levels at pre-treatment are associated with pCR, we will apply two-sample t-tests to compare responders and non-responders. Adjusted P values controlling for false discovery rate (Benjamini and Hochberg method) will be derived. In addition, to assess association of pre-specified immune gene signature with response, the median expression level of the component genes will be used to represent the signature and two-sample t-tests will be used. For genes or signatures that emerge as significantly associated with response, logistic regression models will be used to assess their independent association with response after adjusting for known clinical prognostic factors. To identify pharmacodynamic markers, paired t-test will be carried out to examine immune gene expression differences between pre-treatment and post-treatment samples. Additionally, association of gene expression levels after epigenetic priming with long-term efficacy outcomes, such as PFS and

DFS, will be explored using the Cox proportional hazards regression model. Hierarchical clustering superimposed with response status, relevant baseline or prognostic characteristics or experimental factors will be performed using Spearman correlation and complete linkage to visualize the discriminating power of the immune gene expression and the correlative structure among the genes and the samples.

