#### Genomic Signatures of Response

It is hypothesized that tumors with highly mutated or copy-aberrant genomes will either overexpress native proteins or express novel mutant proteins, both of which may be recognized by the immune system and serve as tumor-specific antigens. Therefore, the effect of genomic mutations on the immune landscape will be investigated in each of the cohorts in this study as follows.

Tumor DNA will be isolated from pre-treatment tissue and post-epigenetic priming specimens and will be analyzed for copy number using the Human Genome CGH 244K Microarray (Agilent, Santa Clara, CA) and/or by next-generation sequencing. Results will be analyzed with DNA Analytics software (Agilent) and with the assistance of the UCSF Genome Core and the UCSF Biostatistics core. For copy number paired Wilcoxon signed-rank test will be applied to test the difference of tumor gene copy number between pre and post-treatment. Two-sample Wilcoxon signed-rank test will be used to test the gene copy number between tumor responders and non-responders for pre-treatment, post-treatment, and changes before and after the treatment, separately. Multiple testing adjustment will be done by controlling false positive rate. Next-generation sequencing will take place using appropriate methods and biostatistical analyses. Annotation will be based on NCBI and UCSC databases. Chi-square test will be applied to obtain the significant variants associated with the clinical response.

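### Two on-treatment marker analyses (antibody change by response, post-priming expression by PFS) do not condition on arm, so if the arms are pooled a vorinostat effect can be mistaken for a response marker

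*Combined protocol and SAP*

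**What the plan says.** All places are in the combined protocol and SAP.

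- **Who is sampled.** Section 3.1: "Follow up biopsies and peripheral blood collection will be taken from all patients post-treatment at 8-10 weeks". Both arms therefore contribute on-treatment material.
- **Antibody arrays (Section 8.3.4.2).** The samples are "sera derived from the pretreatment and after 9 weeks on vorinostat". The number of antibodies with a 2-fold or 4-fold change "will be compared between clinical responders and nonresponders by performing two-sided Wilcoxon rank sum test". Arm is not mentioned.
- **mRNA signatures (Section 8.3.4.1).** A Cox model explores "association of gene expression levels after epigenetic priming with long-term efficacy outcomes", including PFS. No arm term or stratum is given.
- **Genomic signatures (Section 8.3.4.1).** Copy number is compared "between tumor responders and non-responders for pre-treatment, post-treatment, and changes before and after the treatment, separately". The test does not name arm, but the section's introduction speaks of investigating each cohort, which may mean each arm.
- **PD-L1 (Section 8.3.4.1).** Here the logistic model for response does include study arm, next to baseline and Cycle 3 PD-L1.
- **Flow cytometry (Section 8.3.4.2).** This is done arm by arm, but only as a pre-post comparison.
- **Planning rates (Section 8.1.1).** Power is given "when the true response rates are 0.4 and 0.1 for the immune priming and the no immune priming treatment arm".

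**The concern.** Arm can act on both sides of these comparisons. The plan expects vorinostat to raise response, and it expects vorinostat to move immune markers: Section 1.3.1 describes effects on regulatory T cells and PD-L1, and the PD-L1 paragraph of Section 8.3.4.1 says that vorinostat stimulates PD-L1. The antibody metric is itself designed to pick up changes caused by treatment. If patients from both arms are pooled, responders come disproportionately from Arm A, and so do shifted marker values. A purely pharmacodynamic effect can then appear as an association with response or PFS. False discovery rate control does not remove this, because the distortion is confounding and not multiplicity.

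At stake is which markers are carried forward. Section 1.3.1.2 says the pilot could not separate the biomarker's contribution from that of the HDAC inhibitor, because every patient received vorinostat. Pooling over arm would bring back that ambiguity in a trial randomised to resolve it.

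**Working it through.** **1. The plan's own scenario.** The documents give no operating figure for the marker analyses, so the nearest stated figures were reproduced first to fix the setting. Exact enumeration of the two Simon designs gives:

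- Arm A: type I error 0.0249, power 0.904. Arm B: 0.0220 and 0.900. The plan states 0.025 and 0.9 for each.
- Two-sided Fisher test at 0.1, rates 0.4 and 0.1: power 72.44%, against 72.53% stated.
- Probability that Arm A continues at 0.4: 1 − 0.058 = 0.942. Probability that Arm B stops at 0.1: 0.697. Probability of 46 patients (35 + 11): 0.942 × 0.697 = 0.657, against about 65% stated. Probability of 65 patients (35 + 30): 0.942 × 0.303 = 0.285.

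**2. Arm mix by response status.** Expected share of Arm A:

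| Sizes and rates | Among responders | Among non-responders | Difference |
|---|---|---|---|
| 35/11, 0.40/0.10 | 14/(14 + 1.1) = 0.927 | 21/(21 + 9.9) = 0.680 | 0.25 |
| 35/30, 0.40/0.10 | 14/(14 + 3) = 0.824 | 21/(21 + 27) = 0.438 | 0.39 |
| 35/30, 0.40/0.35 | 14/(14 + 10.5) = 0.571 | 21/(21 + 19.5) = 0.519 | 0.05 |

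If vorinostat shifts a marker by d SD and the marker has no link to response within arm, pooling creates a spurious responder minus non-responder difference of about d times the last column.

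**3. False-positive rate of the rank-sum test.** Simulation with 6,000 trials per setting. The marker is normal with mean d in Arm A and 0 in Arm B, response depends on arm only, and the test is two-sided at 0.05. The level, the normal shape and the shifts are assumptions.

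| Setting | d = 1 | d = 2 | d = 3 |
|---|---|---|---|
| 35/11, 0.40/0.10, pooled | 10% | 19% | 24% |
| 35/30, 0.40/0.10, pooled | 23% | 53% | 65% |
| Averaged over the two-stage design, 0.40/0.10, pooled | 13% | 27% | 35% |

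At 0.40/0.35 the pooled test gives 5 to 6% with 35/30 and up to about 7% over the two-stage design. The van Elteren test (Wilcoxon stratified by arm) stays between 4.3 and 5.4%, and Arm A alone between 4.2 and 5.5%.

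**4. Cox model for PFS.** Exponential PFS depending on arm only, marker as in step 3. The hazard ratio (HR) of 0.73 is the one Section 1.3.1.4 reports for adding a different HDAC inhibitor. The HR of 0.5 is an assumption. The HR of 0.40 follows from reading 0.4 and 0.1 as 24-week PFS: ln 0.4 / ln 0.1 = 0.916/2.303 = 0.40.

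| HR | 35/11, d = 1 / 2 | 35/30, d = 1 / 2 |
|---|---|---|
| 0.73 | 7% / 8% | 8% / 15% |
| 0.5 | 10% / 20% | 19% / 46% |
| 0.40 | about 14% / 27% | about 26% / 64% |

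At HR 1.0 the pooled rate is 5 to 6%. Stratified by arm, the Cox test stays between 4.4 and 6.5% across these settings, including those with no marker shift.

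**The case against.** The strongest reply is that pooling is inferred, not stated. Arm B receives no vorinostat, so samples described as "sera derived from the pretreatment and after 9 weeks on vorinostat" could mean Arm A only. Expression after epigenetic priming could likewise exclude the arm that Section 8.1.1 labels as having no immune priming. Section 2.4 also limits the Nanostring and 10x work to arms that succeed. If the tests are run in one arm, the problem does not arise.

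This stands as an ambiguity but does not settle the matter. The flow cytometry paragraph uses the same vorinostat timing for each arm individually, so the phrase does not reliably mean Arm A. The Section 2.4 limit does not mention antibody arrays. Under either reading the plan has to say which arms contribute.

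Other parts of the reply stand in full:

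- The PD-L1 response model already includes arm.
- The copy-number analysis may be by arm, and no section says that vorinostat shifts copy number.
- No section says that vorinostat shifts circulating antibodies in particular, and the antibody endpoint is a count, whereas the simulated marker is normal.
- The 35/30 figures apply to a path with probability of about 0.29 at the planning rates.
- Arm B's own design alternative is 0.35, where the inflation is slight.
- Pre-treatment markers are not confounded by a randomised arm. The mRNA logistic model that seeks "independent association with response after adjusting for known clinical prognostic factors" follows tests of pre-treatment genes, so it needs no arm term on this ground.

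**Conclusion.** The concern holds for the antibody responder test and for the Cox analysis of post-priming expression, provided both arms enter them. It extends to the post-treatment and change comparisons of copy number only if the reference to cohorts does not mean by arm. At the plan's 0.4 and 0.1 rates, the pooled rank-sum test would falsely flag a vorinostat-shifted marker in about 13 to 35% of trials for shifts of 1 to 3 SD, averaged over the two-stage design. The Cox inflation depends on the assumed HR: 7 to 15% at 0.73, and more at about 0.40.

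A reader might infer that every marker vorinostat moves will look like a response marker, or that no on-treatment analysis in the plan adjusts for arm. The documents support neither. The bias needs a marker shift and an outcome difference between arms together. Even with a 3 SD shift, about three quarters of trials on the likeliest path (35/11) would show no false signal. The PD-L1 model is a clear counter-example to the second inference.

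The shifts, the 0.05 level, the normal marker and exponential PFS are assumptions. The analyses are exploratory, and the primary and secondary results are untouched.

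**What to change.** In Section 8.3.4, follow the PD-L1 model's example of accounting for arm:

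- Antibody section: compare responders and non-responders on on-treatment change with a van Elteren test stratified by arm. Do the same for post-treatment and change values of copy number, unless the plan states that these are run by arm.
- mRNA section: stratify the Cox model of post-priming expression by arm.
- Show within-arm results beside each stratified result.
- State which arms supply the samples timed by weeks on vorinostat. If only Arm A is meant, say so.

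No change is needed for pre-treatment markers.

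The cost is SAP wording, with no new data and no change in sample size. The drawback is that if Arm B stops at 11 patients, with 0 or 1 responder by its own rule, it adds little and the stratified result rests mainly on Arm A.
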